**Table 1: Dosage regimen**

Daily dose	
Dose A	50 mg (half a tablet of 100 mg)
Dose B	100 mg (one tablet of 100 mg)
Dose C	150 mg (one and a half tablet of 100 mg)
Dose D	200 mg (two tablets of 100 mg)

Each next dose will start after 14 days of treatment if the previous dose was considered safe by the investigator. The up-titration is based on the following safety criteria, including but not limited to:

- Absence of symptomatic and/or clinically relevant orthostatic hypotension
- SBP > 95 mmHg or DBP > 50 mmHg
- Absence of clinically significant changes in ECG parameters (heart rate, P-R interval, QRS duration, QT and QTc interval)
- Absence of clinically significant hypersensitivity/skin allergic reactions

Patients not fulfilling the criteria for up-titration after 14 days of treatment with 50 mg zamicastat have to be withdrawn from the study.

If the patient's next dose will not be tolerated by the patient, the dose has to be down-titrated to his/her previous dose and this dose will be considered as the individual HTD, if tolerated by the patient. Treatment at the individual HTD will be for 42 days during the maintenance period.

Zamicastat has to be taken in the morning after breakfast. The patient must not take the tablet at home on visit days (A3/B3/C3/D3, MPV1, MPV2 and MPV3).

Patients taking 150 mg or 200 mg of zamicastat and who will not participate in the extension study will take 100 mg zamicastat for 14 days.

In case a patient will discontinue the study early due to the occurrence of an AE, down-titration is not mandatory, but at the investigator's discretion.

## 2.6 Sample Size

The clinical study BIA-51058-201 was designed to explore for the first time the pharmacokinetics, safety and efficacy of zamicastat in PAH patients in its potential therapeutic dose range (50 mg to 200 mg). Since this is an exploratory and descriptive study and no powered comparative statistical analysis is planned, study sample size was not formally calculated. Thus, it was considered that 32 patients constitute an appropriate sample to meet the objectives of the study, considering the low prevalence of the disease and the consequent recruitment constraints.

## 2.7 Blinding

Blinding is not applicable to this study.

### 3 ANALYSIS SETS AND SUBGROUPS

#### 3.1 Analysis Sets

Within the framework of this study, the following analysis sets are defined and analysed:

**The Enrolled Set (ES)** will be defined as all patients who provided informed consent.

**The Safety Set (SS)** will be defined as all patients who belong to ES with at least one IMP administration.

**The Full Analysis Set (FAS)** will be defined as all patients who belong to SS with at least one efficacy assessment at visit MPV3.

**The modified Full Analysis Set (mFAS)** will be defined as all patients who belong to FAS with no substantial changes to their regimen of PAH-approved medications (including diuretics) between visits A1 and MPV3. These patients were defined during Data Review (see Data Review Report, Final 1.0, 10-MAR-2022).

**The Pharmacokinetic Analysis Set (PKS)** and **the Pharmacodynamic (PD) Analysis Set**, as well as all corresponding analyses, are described in the reporting and analysis plan prepared by Quotient Sciences Ltd.

Efficacy analyses will be performed on the FAS and mFAS, and the SS will be used for the analysis of the safety endpoints.

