13.2.2 Full Analysis Set

The full analysis set (FAS) includes all patients with at least one IMP administration.

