13.2.4 Safety Set

The safety set (SS) includes all patients with at least one IMP administration. The FAS and the SS are identical.

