## DOCUMENT REVISION HISTORY

Version Draft 0.1 (09-JUL-2021): Document was created.

Version Draft 0.2 (07-SEP-2021): Document updated after sponsor's review. Notable changes:

- Added table 15.2.5.1 (section 5.5.5)
- Removed the original SF-6D score from analysis (section 5.5.6)
- Added figures 15.2.1 and 15.2.2 (section 5.5.6)
- Added the definition of TEAEs leading to down-titration and table 15.3.1.7 (section 5.6.1)
- Added table 15.3.5.4.2 (section 5.6.5)

Version Draft 0.3 (24-NOV-2021): Document updated after sponsor's review. Notable changes:

- Added specification that the definition of PAH medications will be reviewed during the DRM (section 5.3)
- Updated the range of nominal compliance to 90%-110% (section 5.4.2)
- Added within-visit shift table for ECG abnormalities (section 5.6.5)

Version Draft 0.4 (06-JAN-2022): Document updated after the Data Review meeting and the sponsor's review. Notable changes:

- Changed definition of FAS to only include patients with non-missing efficacy assessments at MPV3 (Section 3.1)
- Added definition of mFAS (Section 3.1). Efficacy analyses will be performed for both the FAS and MFAS (Section 5.5).
- Added definitions for TAPSE subgroups (Section 3.2). TAPSE subgroup analyses will be performed for selected efficacy parameters (Sections 5.5.1, 5.5.2, 5.5.4)
- Safety data will no longer be summarised at derived visit V3. Actual visits will be used (Section 4.4)
- Added definition of PAH-approved medications and corresponding tables (Section 5.3)
- Right heart catheterisation clinical significance assessments will not be used in statistical analysis (Section 5.5.1)
- Added specification that in case the distance covered during both 6MWT attempts is equal, the first attempt will be considered as baseline (Section 5.5.2)
- Changed unit for biomarker NT-proBNP from pg/mL to ng/L (Section 5.5.3)
- Added specification for interpreting normal, NCS abnormal, and CS abnormal findings for arterial blood gas analysis (Section 5.6.3) and ECG (Section 5.6.5)

Version Draft 0.5 (08-FEB-2022): Document updated after sponsor's review. Notable changes:

- Added the coefficient of variance to standard summary statistics (Section 4.1)

Version Draft 0.6 (17-MAR-2022): Document updated after sponsor's review. Notable changes:

- Amended the definition of PAH-approved medications to include diuretics (Sections 3.1, 5.3)

Version Final 1.0 (22-MAR-2022): Document finalised.

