## 2.2.2 Secondary Endpoints

### 2.2.2.1 Safety Endpoints

The safety endpoints of this study are:

1. Adverse events
2. Clinically relevant changes in laboratory parameters (haematology, biochemistry, coagulation, urinalysis, arterial blood gas analysis)
3. Clinically relevant changes in vital signs
4. Clinically relevant changes in physical examination
5. Clinically relevant changes in ECG
6. Number of digital scars (only in patients with scleroderma)
7. Skin score (only in patients with scleroderma)

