## **8 CHANGES TO THE ANALYSIS AS LAID DOWN IN THE PROTOCOL AND AMENDMENTS**

No changes to the analysis as laid down in the clinical study protocol and protocol amendment(s) were made.

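### The SAP's narrowed FAS shuts early leavers out of functional-class shift tables that are meant to run to MPV3/EDV, and SAP Section 8 wrongly reports no changes

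*SAP*

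**What the plan says.** **Protocol.** Section 13.2.2: "The full analysis set (FAS) includes all patients with at least one IMP administration". Section 13.2.4 adds: "The FAS and the SS are identical". Section 13.4.2 bases the efficacy analyses on that set.

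**SAP analysis sets.** Under SAP 3.1 the FAS "will be defined as all patients who belong to SS with at least one efficacy assessment at visit MPV3". The mFAS is the part of the FAS without substantial changes in PAH-approved medication. The section closes: "Efficacy analyses will be performed on the FAS and mFAS, and the SS will be used for the analysis of the safety endpoints".

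**SAP functional class.** SAP 5.5.5 has the class assessed at Visit 1 and at MPV3/EDV. Shift tables 15.2.5.2.1 (FAS) and 15.2.5.2.2 (mFAS) run from V1 to MPV3/EDV. Summary tables 15.2.5.1.1 and 15.2.5.1.2 use the same two sets. Listing 16.2.3.5 shows all functional-class data for the enrolled set.

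**SAP on changes.** Section 8: "No changes to the analysis as laid down in the clinical study protocol and protocol amendment(s) were made". The Document Revision History, however, records the new FAS definition, the mFAS and the TAPSE subgroups under Draft 0.4, described as "Document updated after the Data Review meeting".

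**The concern.** A table that is said to run to MPV3/EDV promises the last assessed class of patients who stopped early. The set on which it is run removes exactly those patients.

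Who they are could matter. The protocol (8.1) requires withdrawal of patients who do not tolerate Dose A, and of patients who do not tolerate their highest tolerated dose during maintenance. The omitted group can therefore include the patients who tolerated the drug worst, in a study that has tolerability among its objectives. Their functional class at EDV is collected by design and then not summarised anywhere.

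The Section 8 statement adds to the problem. A reader who relies on it will take the label Full Analysis Set to mean the protocol's set of all dosed patients.

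**Working it through.** The documents state no figure to reproduce: the 32 patients were not formally calculated (protocol 13.3). The check compares definitions.

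**Step 1: what is measured at EDV.** Protocol 11.6.7 and the schedule mark SF-36v2, the 6-minute walk test, echocardiography, right heart catheterisation and NT-proBNP as not applicable at EDV. WHO functional class carries no such mark, and SAP 5.5.5 schedules it at MPV3/EDV. It is the only efficacy measure collected at EDV.

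**Step 2: whether an EDV can count as MPV3.** Under protocol 11.6.7, a patient who discontinues prematurely has the visit performed as an EDV. SAP Table 4 numbers MPV3 as 530 and EDV as 600. SAP 4.8 analyses by nominal visit number, and no rule maps EDV to MPV3.

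**Step 3: consequence.** EDV instead of MPV3 means no efficacy assessment at MPV3. The patient is then outside the SAP FAS, hence outside the mFAS, and contributes 0 to Tables 15.2.5.2.1 and 15.2.5.2.2. Under the protocol FAS the same patient would be included.

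**Step 4: how the SAP's shift tables are labelled.**

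| Shift tables | Set | Number | Stated end point |
|---|---|---|---|
| Catheterisation, echocardiography, SF-36v2 | FAS, mFAS | 2 + 2 + 2 = 6 | MPV3 |
| Functional class | FAS, mFAS | 2 | MPV3/EDV |
| Haematology, biochemistry, coagulation, urinalysis, ECG (15.3.5.4.2) | SS | 4 + 1 = 5 | MPV3/EDV |
| Arterial blood gas (15.3.3.3) | SS | 1 | MPV3/EDV |

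Of the 6 + 2 = 8 shift tables on the FAS or mFAS, 2 name EDV. The last row shows that the label alone proves little: blood gas is not done at EDV (protocol 11.6.7; SAP 5.6.3 schedules it at A1 and MPV3 only).

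**Step 5: what does not move.** The efficacy endpoints are changes from baseline to MPV3 (protocol 13.1.2.2, SAP 2.2.2.2). The protocol uses observed cases (13.2.5) and the SAP imputes nothing (4.10). A patient without an MPV3 value contributes no such change under either FAS.

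**Step 6: illustration on assumed inputs.** Assume 32 dosed patients, 5% to 30% of them with an EDV and no MPV3, and 2 patients with a worse class at MPV3.

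- At 5%: 32 × 0.05 = 1.6, about 2 patients left out. The table would show 2/30 = 6.7%. Among all dosed patients the figure would lie between 2/32 = 6.25% (no EDV patient worse) and 4/32 = 12.5% (all worse).
- At 30%: 32 × 0.30 = 9.6, about 10 left out. The table would show 2/22 = 9.1%, against 2/32 = 6.25% to 12/32 = 37.5%.

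The table's figure lies inside the range in both cases, so the direction is not determined. None of these percentages estimates what happened in this trial.

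**Step 7: Section 8 against the text.**

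| Item | Protocol | SAP | Kind |
|---|---|---|---|
| FAS | All dosed (13.2.2) | Also needs an MPV3 efficacy assessment (3.1) | Departure |
| mFAS | Not present | 3.1 | Addition |
| TAPSE subgroups | Not present | 3.2 | Addition |
| Physical examination | Assessed, not listed as an endpoint (13.1.2.1) | Listed: "Clinically relevant changes in physical examination" (2.2.2.1) | Addition |
| PD analysis | On the pharmacokinetic set (13.4.5) | Separate PD Analysis Set named (3.1) | Addition |

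That is one departure and four additions, against none declared. The PD set is defined in a separate plan, so its membership cannot be compared here.

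**The case against.** The best counter-argument is that MPV3/EDV in the functional-class tables is only the visit-column name, left in place when Draft 0.4 narrowed the FAS. The blood-gas table shows that the SAP uses this label where no EDV data are scheduled. On that view, changing the label to MPV3 is enough and matches the defined endpoint. This stands in part: a reader might infer from the other efficacy tables that the EDV label was deliberate, and the documents do not establish that. But functional class, unlike blood gas, is scheduled at EDV. Relabelling alone would remove the contradiction and leave collected data unsummarised.

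It can also be said that the protocol calls its statistics section a summary and leaves details to the SAP (section 13), and that the SAP declares that it supersedes the protocol's statistical considerations (Introduction). That gives the SAP authority to change the FAS. It does not make a statement of no changes true.

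Finally, the new definition is stated openly in SAP 3.1 and in the revision history. Table 15.1.1.2 gives exclusions with reasons, and the EDV classes remain in Listing 16.2.3.5. All of this stands. A reader might infer concealment from Section 8, and the open record speaks against it.

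**Conclusion.** The point holds as an internal mismatch and an incorrect Section 8, and both should be corrected. Two tables have a stated span that their analysis set cannot fill, and the matching summary tables leave out the same patients. This rests on EDV and MPV3 being distinct nominal visits, as SAP Table 4 and section 4.8 have it.

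Two stronger readings are tempting and unsupported. One is that narrowing the FAS biases the efficacy results: no change-to-MPV3 result differs between the two sets. The other is that the omission flatters the functional-class picture: neither the number of patients with an EDV instead of MPV3 nor their class is given, so size and direction are unknown. The study is descriptive, with no powered comparison, so no formal inference is at risk.

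**What to change.** 1. Produce the functional-class shift table and the matching summary table (15.2.5.1.x) on the SS, which is the protocol's FAS. Show EDV as its own category beside MPV3, neither pooled with it nor carried forward. Amend the last sentence of SAP 3.1 to allow this. Keep the FAS and mFAS versions and label them V1 to MPV3.
2. Rewrite Section 8. Declare and justify the FAS redefinition as a departure from the protocol. List the mFAS, the TAPSE subgroups, the physical-examination endpoint and the separate PD Analysis Set as additions. Note that the FAS change, the mFAS and the TAPSE subgroups came in after the data review meeting of an open-label study.

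The change-to-MPV3 tables stay as they are. The cost is a few sentences in SAP 3.1, 5.5.5 and 8, and one or two tables from data already collected.

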9.2 Inclusion Criteria

At **Visit 1 (Screening)**, patients must meet ALL of the following criteria:

1. Male or female patients aged 18 to 75 years, inclusive.
2. Able to comprehend and willing to sign an informed consent form (ICF).
3. Diagnosis of PAH (pulmonary arterial hypertension WHO Group 1) documented by RHC with a mPAP \geq 25 mmHg, a PAWP \leq 15 mmHg and a PVR $>$ 3 WU [8,9]:
 - a) Idiopathic, in non-vasoreactive patients
 - b) Heritable: Bone morphogenetic protein receptor type II (BMPR2) mutation and other mutations, in non-vasoreactive patients
 - c) Drugs and toxin induced, in non-vasoreactive patients
 - d) Associated with connective tissue disease
 - e) Associated with simple congenital defects (atrial septal defect and/or ventricular septal defect) if closed $>$ 12 months before inclusion.
4. The patient's last right heart catheterisation results, which were measured at the study site, must not be older than 90 days before V1 (will be considered as baseline value). Otherwise a right heart catheterisation has to be performed as part of the study at visit A1.
5. WHO functional class II or III as judged by the investigator.
6. Stable treatment with at least one of the following approved PAH therapies for at least 90 days prior to V1: Ambrisentan, Bosentan, Macitentan, Riociguat, Selexipag, Sildenafil, Tadalafil, Epoprostenol intravenous, Iloprost inhaled or Treprostinil intravenous or subcutaneous.
7. For women: Agree not to donate ova from the time of informed consent until 30 days after the last IMP intake.
For men: Agree not to donate sperm from the time of informed consent until 90 days after the last IMP intake.

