11.4.4 Right heart catheterisation

Right heart catheterisation will be performed at visit A1, unless an RHC was performed within 90 days before visit V1 at the study site and the result of the following parameters is available: PVR, right atrial pressure (RAP), mPAP, cardiac index (CI) and mixed venous oxygen saturation (SvO₂%). Additionally, an RHC will be performed at MPV3 to determine the change of haemodynamic parameters in the patients. The RHC has to be performed before IMP intake. The following haemodynamic parameters will be determined:

- Cardiac output (CO, L/min)
- Mixed venous oxygen saturation (SvO₂%)
- Pulmonary artery pressure systolic, diastolic and mean (PAPs, PAPd and mPAP, mmHg)
- Pulmonary artery wedge pressure (PAWP, mmHg)
- Right atrial pressure (RAP, mmHg)
- Transpulmonary pressure gradient (TPG, mean PAP – mean PCWP)
- Diastolic pressure gradient (DPG, diastolic PAP – mean PCWP)
- Pulmonary vascular resistance (PVR; dyn x s x cm⁻⁵)
- Systemic vascular resistance (SVR, dyn · s/cm⁵)
- Cardiac index (CI, L/min/m²)
- Pulmonary arterial compliance (PAC; SV/PP, mL/mmHg)
- Heart rate (bpm)
- Stroke volume (mL/beat)
- Stroke volume index (mL/m²)

RHC will be performed according to the standard procedures provided in the 2015 ESC/ERS Guidelines for the diagnosis and treatment of pulmonary hypertension. [8]

If data from an RHC within 90 days before visit V1 are available, which were measured at the study site, the available data points will be transcribed to the eCRF and the procedure will not be repeated at visit A1.

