**Table 4: Visit Names and Labels**

Period	Number	Name	Description	Label in TLFs
Screening	100	Visit 1	Screening visit. Day -12 to -5	V1
Dose finding	110	Visit A1	Day 1	A1
	120	Visit A2	8 days $\pm$ 2 after A1 (phone call)	A2
	130	Visit A3	14 days $\pm$ 2 after A1	A3
	220	Visit B2	8 days $\pm$ 2 after A3 (phone call)	B2
	230	Visit B3	14 days $\pm$ 2 after A3	B3
	320	Visit C2	8 days $\pm$ 2 after B3 (phone call)	C2
	330	Visit C3	14 days $\pm$ 2 after B3	C3
	420	Visit D2	8 days $\pm$ 2 after C3 (phone call)	D2
Maintenance	430	Visit D3	14 days $\pm$ 2 after C3	D3
	510	Visit MPV1	13 days $\pm$ 2 after D3/UV for down-titration	MPV1
	520	Visit MPV2	27 days $\pm$ 2 after D3/UV for down-titration	MPV2
Dose finding/ Maintenance	530	Visit MPV3	41 days $\pm$ 2 after D3/UV for down-titration	MPV3
	600	Early Discontinuation Visit	Within 10 days of early discontinuation	EDV
Follow-up	610	Follow-up visit [down-titration]	14 days $\pm$ 2 after MPV3/EDV (phone call)	FUV1
	620	Follow-up visit	14 days $\pm$ 2 after last IMP intake	FUV2

Unscheduled visits (UV) will be numbered and labelled based on the preceding scheduled visit, e.g. "UV A1.1" for the first unscheduled visit after the scheduled visit A1. Multiple unscheduled visits after the same scheduled visit will be numbered and labelled sequentially.

For patients attending the extension study, adverse events and concomitant medications will only be displayed up to the end date of visit MPV3.

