## 4.5 Day Numbering

All assessment dates will be related to the date of first IMP intake. The date of first IMP intake is referred to as Day 1. Day -1 is the day preceding Day 1 and Day 0 will not be defined. The numbering is such that Day -2 is the day before Day -1, Day 2 is the day after the first IMP intake, etc.

Treatment days may alternatively be numbered with reference to the ongoing study period using the following rules:

- Dates prior to the first IMP intake will be numbered with reference to the date of first IMP intake as described above.
- Dates after the first IMP intake will be numbered with reference to the first day of the ongoing study period using the same rules as described above. Study days during the dose-finding period will be prefixed with the corresponding dose letter (e.g. C-11 for day 11 on the 150 mg dose), study days in the maintenance period will be prefixed with the letter M, and study days in the post-maintenance periods will be prefixed with “DT” and “FU” for the down-titration period and the follow-up period respectively.

For definitions of the study periods, see section 4.6.

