## 4.7 Baseline Value

### Baseline value

The baseline value for a variable is defined as the last non-missing value collected before the first IMP intake, unless otherwise specified.

See section 5.4.1 Exposure to IMP for definition of first IMP intake.

**Absolute change from baseline** will be calculated as

$$\text{Absolute Change from Baseline at Visit } X = \text{Value at Visit } X - \text{Baseline Value}$$

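### The mFAS screens for PAH-therapy changes only from A1, but the change-from-baseline window opens before A1 for V1-based endpoints and for historical RHC baselines

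*SAP*

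**What the plan says.** **Screening window.** The mFAS is the FAS restricted to patients with "no substantial changes to their regimen of PAH-approved medications (including diuretics) between visits A1 and MPV3" (SAP 3.1). Its members were identified at Data Review. Diuretics count as PAH-approved medication for this purpose (SAP 3.1 and 5.3).

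**Endpoints and baselines.** The efficacy endpoints are changes from baseline to MPV3 (SAP 2.2.2.2). The general baseline is "the last non-missing value collected before the first IMP intake, unless otherwise specified" (SAP 4.7).
- 6-MWT, NT-proBNP, echocardiography, functional class and SF-36v2 are measured before treatment only at V1 (SAP 5.5.2 to 5.5.6). SAP Table 4 describes V1 as "Screening visit. Day -12 to -5".
- For haemodynamics, "Right heart catheterisation will be performed at visit A1, unless an RHC was performed within 90 days before visit V1 at the study site" (Protocol 11.4.4). When such a result exists it becomes the baseline (Protocol 9.2, criterion 4), and the procedure is not repeated at A1.

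**Eligibility.** Criterion 6 asks for "Stable treatment with at least one of the following approved PAH therapies for at least 90 days prior to V1" (Protocol 9.2). The drugs it names do not include diuretics.

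**Medication data.** Drug, daily dose, and start and stop dates are collected. All medications go into Listing 16.2.1.8, and prior PAH medications have their own tables. The by-visit table of PAH-approved therapy shows A1 and MPV3 only (SAP 5.3).

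**The concern.** The mFAS is the only efficacy set that removes patients because their background therapy changed. For that to work, the screening window must match the interval over which change is measured. It starts later for every endpoint with a V1 baseline and for every patient with a historical RHC baseline.

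Suppose a patient's diuretic or second PAH drug is changed after the baseline RHC but before A1. The patient stays in the mFAS, and any haemodynamic effect of that change falls inside the reported change from baseline. The study is open-label with no control arm, so nothing else in the design separates such an effect from that of zamicastat. The TAPSE-subgroup tables for RHC, 6-MWT distance and echocardiography are specified on the mFAS alone (SAP 5.5.1, 5.5.2, 5.5.4), so they have no FAS counterpart to compare with.

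**Working it through.** The plan gives no figure of its own on this point, so the check is calendar arithmetic on nominal visit times, ignoring the ±2-day windows.

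**Inputs**
- V1 falls on Day -12 to -5 (SAP Table 4). Because "Day -1 is the day preceding Day 1 and Day 0 will not be defined" (SAP 4.5), these days are 12 and 5 days before A1.
- Oldest historical RHC usable as baseline: 90 days before V1 (Protocol 9.2, criterion 4; Protocol 11.4.4).
- Dose-finding steps last 14 days each, with up to four steps. MPV3 is 41 days after D3 or after down-titration (SAP Table 4).

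**Step 1: days between baseline and A1**
- V1-based endpoints: 5 to 12 days.
- Oldest historical RHC: 90 + 5 = 95 to 90 + 12 = 102 days.
- RHC done at A1: 0 days.

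**Step 2: days that the mFAS does screen, A1 to MPV3**
- All four dose steps completed: 4 × 14 + 41 = 97 days.
- Shortest case, down-titration to 50 mg as soon as the second step begins: 14 + 41 = 55 days.

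**Step 3: share of the baseline-to-MPV3 interval left unscreened**

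Share = days before A1 / (days before A1 + days from A1 to MPV3).

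| Baseline | Full dose sequence (97 days) | Earliest down-titration (55 days) |
|---|---|---|
| V1, 5 days before A1 | 5/102 = 4.9% | 5/60 = 8.3% |
| V1, 12 days before A1 | 12/109 = 11.0% | 12/67 = 17.9% |
| Oldest RHC, 102 days before A1 | 102/199 = 51.3% | 102/157 = 65.0% |
| RHC at A1 | 0% | 0% |

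**Step 4: what inclusion criterion 6 covers**

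The criterion's 90 days before V1 match the RHC look-back, so it has to be credited. It can be read in two ways: the whole PAH regimen is stable, or at least one listed drug is stable.

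| Interval | Listed drugs, whole-regimen reading | Listed drugs, literal reading | Diuretics |
|---|---|---|---|
| Historical RHC to V1 (up to 90 days) | covered | one drug covered; a second may change | not covered |
| V1 to A1 (5 to 12 days) | not covered | not covered | not covered |

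The longest unprotected span is therefore 12 days for listed drugs on the whole-regimen reading. It is 102 days for diuretics and, on the literal reading, for a second PAH drug.

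The eligibility re-check at A1 (SAP 5.1.3) does not extend the cover, because the criterion itself ends at V1. Nor does a breach of criterion 6 automatically remove a patient from the mFAS. It is classed for case-by-case review (PD#06), and the only set exclusion that SAP Section 6 attaches to a major deviation is from the pharmacokinetic set.

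**The case against.** The other side has four good arguments.

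1. **Changes before A1 are not hidden.** A reader might infer that they go unseen. The documents do not support that: medications are collected with dates and doses, listed in full, and prior PAH medications are tabulated. What stands is narrower: these records do not decide mFAS membership, and the by-visit therapy table does not show the period before A1.
2. **Half the interval is a corner case.** A reader might take 51% as typical. It needs a historical RHC exactly 90 days before V1 and V1 exactly on Day -12. The default RHC is at A1, with no gap, and the number of patients with a historical RHC is not given. Nor is 51% an absolute ceiling, since it assumes the full dose sequence. For the other five efficacy domains the gap is 5 to 12 days.
3. **Criterion 6 already covers much of the RHC gap.** On the whole-regimen reading this is right for the listed drugs up to V1. It does not help for diuretics, which the sponsor added to the PAH-approved definition in SAP Draft 0.6, or for V1 to A1.
4. **Efficacy is secondary and exploratory, and FAS results are reported too.** This limits the consequence. Even a perfectly defined mFAS would not let an uncontrolled change be attributed to zamicastat. It remains true that the set does not fully do what it was added to do.

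The Data Review Report that applied the rule is not among the documents. It may have considered changes before A1, but the SAP definition does not ask for that.

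**Conclusion.** The point holds as a mismatch between the mFAS window and the change-from-baseline window. It deserves correction but does not undermine the study. The unscreened part is 5 to 12 days for the V1-based endpoints (4.9% to 11.0% of the interval at the full dose sequence, up to 17.9% with the earliest down-titration). For haemodynamics it is nil when the RHC is done at A1, and at most 102 days with a historical RHC (51.3%, or 65.0% with the earliest down-titration).

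These figures assume nominal visit times and the Protocol Version 3.0 rules, on which the SAP is based. They measure unscreened time, not bias. The documents do not say how many patients used a historical RHC or changed therapy before A1, so the effect on any estimate cannot be computed. A reader might conclude that the mFAS results are in fact distorted; nothing in the documents shows that.

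**What to change.** In SAP 3.1, define the mFAS window separately for each endpoint: from the date of the baseline assessment actually used to MPV3. That means the RHC date for haemodynamics and V1 for 6-MWT, NT-proBNP, echocardiography, functional class and SF-36v2. Reapply the rule with the medication start and stop dates already in the eCRF, keeping the Data Review's judgement of what counts as a substantial change, so that only the window differs.

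A single window from the earlier of the RHC date and V1 would be wrong. It would drop patients from V1-based analyses for changes made before those baselines were taken.

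Report how many FAS patients had a qualifying change between baseline and A1, split into diuretics and listed PAH drugs. Show the new results beside the A1-to-MPV3 mFAS already defined. The mFAS was added after the Data Review meeting (SAP revision history, Draft 0.4), and showing both keeps a further redefinition transparent.

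The cost is one revised definition and a rerun of the medication check and the mFAS tables, with no new data collection. The mFAS may lose a few patients from a planned 32, and its membership may differ between RHC and the other endpoints, so each table needs its own denominator. The documents state no look-back period for recording prior medication. Where a record does not reach back to the RHC date, the patient should be flagged as not assessable rather than assumed stable.
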